8.8 Known drug reactions and interaction with other therapies

Table 8 - medications known to interact with doxycycline and prohibited from being taken during the intervention

Medication name	
Warfarin	
Penicillin	
Antacids containing aluminium, calcium, magnesium or other drugs containing	these
cations; oral zinc, iron salts or bismuth preparations	
Barbiturates, carbamazepine, primidone, phenytoin	
Methoxyflurane(used as inhalation anaesthesia in emergency departments or pr	ior to
surgery)	
Ciclosporin	
Rifampicin	
Ergotamine	
Methysergide	
Methotrexate	
Kaolin	
Sucralfate	
Quinapril	
Oral contraceptives	
Retinoids (vitamin A or retinoids. Retinol, retinal, tretinoin (retinoic acid), isotret alitretinoin, etretinate, acitretin, adapalene, bexarotene, and tazarotene)	inoin
Oral typhoid vaccines	
Fluorescence test	
Drugs with the potential to cause hepatotoxicity should be avoided.	
Avoid retinoids and vitamin A.	
Caution in use of creams that contain vitamin A or retinoids: retinol, retinal, tre	tinoir
(retinoic acid), isotretinoin, alitretinoin, etretinate, acitretin, adapalene, bexaroten	e, and
tazarotene.	

8.9 Concomitant medication

Avoid alcohol and drugs with the potential to cause hepatotoxicity.

8.10 Trial restrictions

There are no specific dietary restrictions.

Participants must not use oral contraception and instead use barrier contraception or refrain from unprotected intercourse from the menstrual cycle prior to screening and for the duration of treatment.

8.11 Assessment of compliance with treatment

Participants will be asked to return any medication at the end of treatment. Any medication returned will be sent to pharmacy and recorded on the accountability log.

Participants will be required to keep a treatment diary of doses taken and document any missed doses. Treatment compliance will be reviewed within six weeks following randomisation (in-person or via telephone). At the end of the patient's participation in the trial any used IMP will be returned to pharmacy to be counted and destroyed.

9. TRIAL ASSESSMENTS

Please refer to the Table 5 CERM Schedule of Events which outlines the assessments at each trial Visit.

Details of all trial assessments should be written in the participants medical notes.

9.1 Screening and Registration

The following assessments should be completed during the screening and registration phase of the trial to evaluate patient eligibility. Written informed consent must be obtained prior to any trial specific assessments or investigations taking place.

- Demographics
- BMI (Height & Weight)
- Smoking history
- Medical History
- Obstetric History
- Pregnancy History
- Concomitant medication review
- Pregnancy Test
- Contraception review
- Period review

9.2 Screening

Following registration all participants will have the following assessments:

• Endometrial Biopsy

The endometrial biopsy should be handled as specified in the tissue sample section of the protocol.

9.2.1 CERM B (UHCW only n~400 participants)

- Vaginal Swab
- Endometrial Swab
- Cervical Swab

This should be taken at the same time as the Endometrial Biopsy.

9.3 Randomised Controlled Trial

The following assessments should be completed during the randomisation phase of the trial to evaluate patient eligibility. Written informed consent must be obtained for the

randomised controlled trial prior to any RCT trial specific assessments or investigations taking place.

- Confirmation of CE
- Concomitant medication review
- Pregnancy Test
- Contraception review
- Period review
- Adverse Events

CERM B participants should be provided with a second biopsy preparation kit. CERM B participants with a positive CE result should be reminded to contact the clinic when they are ovulating or if the test does not indicate ovulation on day 23, to arrange to come into clinic for a second biopsy.

9.4 Treatment completion

The following assessments should be completed (via telephone) within 6 weeks post randomisation and captured on the Treatment Completion Form:

- Daily dosage of drug
- Check if the participant has missed any doses
- Check if participant completed the full course of treatment
- Adverse Events
- Concomitant medication review
- Contraception review
- Pregnancy confirmation (if applicable)

Participants should be reminded to return their treatment diary and to take any unused medication back to pharmacy.

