2.3.1 Risk of Pregnancy

In the summary of product characteristics (SPC) doxycycline is contra-indicated in pregnancy, because tetracycline use has been associated with problems with infant's teeth and bone development. However, a meta-analysis by Cross and colleagues (2016)³⁴ reported an absence of evidence of harmful effects when taken in pregnancy and there are no known reported cases or evidence of harm from taking doxycycline from day 1 to 14 of the menstrual cycle. Doxycycline is prescribed to pregnant women "when travel to malarious areas is unavoidable during pregnancy, doxycycline can be used for malaria prophylaxis if other regimes are unsuitable, and if the entire course of doxycycline can be completed before 15 weeks' gestation" (BNF, 2018-2019). This trial has been designed so there is minimal chance of fetal exposure in the following ways:

- **1.** A pregnancy test is performed prior to taking doxycycline
- **2.** Doxycycline/placebo is taken on the first day of the menstrual cycle so women are not pregnant when they start taking the intervention
- **3.** The doxycycline/placebo are taken prior to ovulation, hence before pregnancy is possible we review all women's cycles
- 4. Women are advised and consent to use condoms
- **5.** The half-life of doxycycline is 16-22 hours thus there will be minimal drug present one week after the drug is stopped should implantation occur.¹⁰

The doxycycline/placebo will start on the first day of their next menstrual cycle. We plan to start the intervention on day one of the cycle to ensure that the treatment is completed during the proliferative phase of the cycle, thus negating the risk of doxycycline exposure in early pregnancy.

If a participant reports she is pregnant during the month they are taking the doxycycline/placebo, they will discontinue taking the doxycycline/placebo and will be reassured that the risk to her infant is extremely small.

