7.7 Randomisation – Randomised Controlled Trial

The trial ID number allocated during registration will be used as part of the randomisation process.

Sites should log on to the CERM registration/randomisation portal to randomise the participant and obtain a drug pack number. Sites should access the portal via the link below:

https://ctu.warwick.ac.uk/CERM

In the unlikely event the registration/randomisation portal is not available please contact the WCTU CERM Trial Team (contact details given in table 4) who will be available week days between 09:00 and 17:00 (16:00 on Fridays).

Women will be randomised using minimisation, balancing age and number of previous miscarriages, as these are the two most important predictors of pregnancy outcome in women with RM.

An email will be sent to the PI and lead contact at site confirming participant randomisation details, trial ID number and participant drug pack number.

Following randomisation the site research team should ensure that the participant's details are updated onto the local site's participant enrolment Log.

Once a participant is randomised they should be provided with the 'Taking my capsules on the CERM trial: Chronic Endometritis and Recurrent Miscarriage' leaflet and instructed as follows:

- Take one capsule, twice a day, 12 hours apart for 14 days starting on day one of their menstrual cycle.
- Use condoms and to not have unprotected sexual intercourse during their entire menstrual cycle and not just whilst taking the doxycycline/placebo. This is the last cycle women will be asked to use condoms and to not have unprotected sexual intercourse.
- Given a CERM Trial participant card. This should be carried with the participant at all times. If a replacement is needed they should contact their local site research team.
- Participants should be reminded to undergo a urine pregnancy test as soon as their menstrual periods are delayed or a pregnancy is suspected and to contact the site research team immediately.

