10.3 Recording and reporting of AEs SAEs, SARs AND SUSARs

AEs and SAEs will be collected from the time of written consent for randomisation until 30 days post last trial treatment (last capsule taken). AEs and SAEs will not be collected for participants who do not have CE.

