10.3.1 Recording of Adverse Events

All AEs (except those specified in table 9) that occur in either the participant, fetus or infant should be recorded on an Adverse Event Form and in the participants' medical notes.

If the AE is ongoing at the time of reporting then any change to the condition or outcome of the event should be reported on an Adverse Event Follow-up Form.

30 days after the participant has completed their treatment there is no requirement for the hospital research team to identify any new AEs. However, if the hospital research team become aware of an SAE that has occurred post 30 days since last treatment received and the Investigator considers the SAE to be related to doxycycline/placebo, then the Investigator should report the SAE.

Adverse Event data will be reviewed by the CERM TMG and by the DMC.

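### The treatment-completion and adverse-event call is counted from randomisation, not from the last capsule, so for every full-course participant its deadline falls before the 30-day adverse-event window ends

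*Protocol*

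**What the plan says.** Two sections of the protocol time the post-treatment check from randomisation. Section 9.4 has "The following assessments should be completed (via telephone) within 6 weeks post randomisation", covering daily dosage, missed doses, completion of the course, AEs, concomitant medication and contraception. Section 8.11 repeats the anchor: "Treatment compliance will be reviewed within six weeks following randomisation".

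Treatment does not start at randomisation. Section 2.3.1 says "The doxycycline/placebo will start on the first day of their next menstrual cycle", and section 7.7 instructs women to "Take one capsule, twice a day, 12 hours apart for 14 days starting on day one of their menstrual cycle". The three-month limit in section 6.4 applies to the time before randomisation. Nothing limits the wait after it.

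The AE period is tied to the last capsule. Section 10.3 says "AEs and SAEs will be collected from the time of written consent for randomisation until 30 days post last trial treatment (last capsule taken". Section 10.3.1 lifts the duty to look for events only after that: "30 days after the participant has completed their treatment there is no requirement for the hospital research team to identify any new AEs".

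Three other provisions bear on the point:
- Table 5 marks an adverse event review at Randomisation, Treatment completion and Pregnancy Review. Section 10.4 makes the PI responsible for checking for AEs when participants are contacted for follow-up.
- Section 9.5 lists what is asked at each later contact: whether the woman is trying to conceive, her pregnancy status and the pregnancy outcome. AEs are not on that list. Section 9.5.2 schedules these contacts every three months from the treatment-completion assessment.
- Section 9.4.1 has CERM B women complete the 9.4 items at the second biopsy visit, 10 ± 4 days after ovulation.

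**The concern.** The deadline and the thing it should capture are counted from different days. The deadline runs from randomisation. The course, and the AE period that follows it, run from a menses that may come weeks later. A site that keeps to 9.4 therefore makes its only scheduled post-treatment AE call before the protocol's own AE period has ended, and in some women before dosing has ended.

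What is at stake is the completeness of AE and compliance data. AE data go to the Trial Management Group and the Data Monitoring Committee (DMC). If the late part of the window is picked up only at a contact about three months later, minor events will be forgotten or misdated. Sites also face two instructions for CERM B that cannot always both be met.

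**Working it through.** **Inputs.** Call deadline: 42 days after randomisation (8.11, 9.4). Course: 14 days from cycle day one (2.3.1, 7.7). AE window: 30 days after the last capsule (10.3). Section 6.2 excludes cycles of 21 days or less and of 42 days or more, so eligible cycles run 22 to 41 days and w is roughly 0 to 41 days. The protocol gives no derivation of the six weeks, so there is no figure to reproduce. It happens to equal a 28-day wait plus a 14-day course (28 + 14 = 42), which leaves nothing for the AE window.

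**Day count for a full course**, with day 0 = randomisation:
- first capsule: day w
- last capsule: day w + 13
- end of AE window: day w + 13 + 30 = w + 43
- shortfall of a day-42 call: (w + 43) − 42 = w + 1 days

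| w | last capsule | AE window ends | shortfall at day 42 |
|---|---|---|---|
| 0 | day 13 | day 43 | 1 day |
| 14 | day 27 | day 57 | 15 days |
| 28 | day 41 | day 71 | 29 days |
| 30 | day 43 | day 73 | all 30 post-treatment days |

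If the first capsule is an evening dose, the last falls on day w + 14 and each shortfall grows by one day, up to the full 30. Six weeks is an upper limit, so an earlier call leaves more uncovered.

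**Last capsule after the deadline.** w + 13 > 42 requires w ≥ 30. Assume w is uniform on 0 to L − 1 for cycle length L (the documents do not give its distribution):
- L = 28: 0%
- L = 35: 5/35 = 14%
- L = 41: 11/41 = 27%

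With an evening start the threshold is w ≥ 29, which gives 0%, 6/35 = 17% and 12/41 = 29%.

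**Average uncovered part of the 30 days.** On the same assumption, with the call made exactly on day 42, the uncovered days are the smaller of w + 1 and 30. The means are 14.5 days (L = 28), 17.6 (L = 35) and 19.4 (L = 41).

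**Early discontinuation.** If dosing stops after d days, the last capsule is on day w + d − 1 and the window ends on day w + d + 29. That is on or before day 42 when w + d ≤ 13. For example, a woman who starts on day 3 and stops after 10 days is fully covered by a day-42 call.

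**Next contact.** Taking three months as 91 days, a day-42 call puts the next contact near day 42 + 91 = 133. For full-course women that is roughly 50 to 90 days after the AE window has closed.

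**CERM B.** Assuming ovulation near cycle day 14 (day w + 13 on this count), the second biopsy visit falls on day w + 19 to w + 27. Its late end passes day 42 once w exceeds 15, and its early end once w exceeds 23.

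**The case against.** The best reply is that AE collection does not close with this call. Table 5, which section 9 names as the outline of assessments, marks a further AE review at Pregnancy Review, and section 10.4 requires checks at follow-up contacts. AEs have their own form and follow-up form, and serious events go to the trials unit within 24 hours of awareness. This stands: a reader might infer that late AEs are lost, and the documents do not support that. What remains is delay, recall, and a 9.5 list that omits an item Table 5 contains.

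A reader might also infer that the window is missed in every participant. That fails, because it runs from the last capsule actually taken, section 8.7 lists several reasons for stopping, and women with w + d ≤ 13 are covered.

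The uncovered days are also the late ones. Section 2.3.1 gives a half-life of 16 to 22 hours. On the uniform assumption, a day-42 call in a 28-day cycle reaches at least 7 days past the last capsule when w ≤ 22, which is 23/28 = 82% of women. This limits the harm but does not reconcile 9.4 with 10.3.

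Finally, a later call has its own cost. It moves the near-treatment check on dosing further from the dosing. That is fair and belongs with the fix. Keeping the six-week call and only adding AEs to 9.5 would be simpler, but it would leave late events to recall at about three months and some calls due before the last capsule.

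**Conclusion.** The anchor is wrong. For every participant who takes the full 14 days, the call deadline precedes the end of the stated AE window by at least 1 day. This follows from the protocol's own figures and needs no assumption about w. The typical size does depend on w: about half of the 30 days uncovered on average in 28-day cycles, if randomisation is spread evenly over the cycle.

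A last capsule after day 42 is confined to waits of 30 days or more, meaning long cycles with randomisation soon after menses began. The shares above hold within a given cycle length. No trial-wide share can be stated, because the documents give no distribution of cycle lengths.

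Two stronger conclusions are tempting and are not shown:
- **A distorted DMC comparison between arms.** The trial is double-blind and the timing is the same in both arms, so the expected effect is under-ascertainment and recall error in both alike.
- **Missed drug exposure in early pregnancy.** Sections 7.7 and 9.5 tell women to test when a period is delayed and to contact the site at once, independently of this call.

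Severity is minor to moderate.

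**What to change.** 1. In 8.11, 9.4 and Table 5, count the completion and AE call from the last capsule taken, with the date from the treatment diary, instead of from randomisation. Time it at or just after 30 days post last capsule. For a full course this is no earlier than day w + 43: day 43 at w = 0, day 71 at w = 28 and day 84 at w = 41.
2. In 9.5, list the AE review that Table 5 already marks, and ask specifically about the period up to 30 days after the last capsule.
3. Reconcile 9.4.1 with this timing. CERM B women can complete the dosing items at the biopsy visit and the AE items at a short later call or at the next contact.

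The cost is wording in these sections and a change to the reminder schedule. The call comes later, so the dosing and missed-dose items lean more on the diary that women already keep. CERM B women may need one short extra call. No change to treatment is involved.

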9.4.1 CERM B participant post treatment completion – UHCW ONLY

In addition to the assessments listed in section 9.4 CERM B participants (n^{200}) will undergo the following assessments 10 (+/- 4) days after ovulation following treatment completion:

- Pregnancy test
- Period review
- Endometrial Biopsy
- Vaginal Swab
- Endometrial Swab
- Cervical Swab

The UHCW research team will keep in regular contact with these participants.

Participants should be asked to bring in their treatment diary and any unused medication. Treatment completion assessments listed in 9.4 will be competed at this visit.

9.5 Pregnancy review

Participants should be reminded to undergo a urine pregnancy test as soon as their menstrual periods are delayed or a pregnancy is suspected and to contact the site research team immediately.

Communication with participants will then be via telephone until a urine pregnancy test is positive (as per local policy). At each contact a member of the hospital research team will check if participants are trying to conceive, their pregnancy status and pregnancy outcome.

9.5.1 Women wo do not have CE and are not randomised

Research staff at site should contact participants every 3 months via telephone, from the date of biopsy result until first pregnancy outcome or demise or until 12 months post biopsy result if the participant does not report a pregnancy in this time. Details of any confirmed first pregnancies should be recorded. Information on gestation and pregnancy outcome only i.e. miscarriage, live birth, stillbirth will be collected and recorded.

9.5.2 Women with CE who are randomised

Research staff at site should contact randomised participants every 3 months via telephone, from the treatment completion assessment date, until 6-8 weeks post pregnancy (>24 weeks gestation) or until the trial ends. Research staff should schedule in these calls with participants at each contact.

If a randomised participant confirms pregnancy they should be contacted at the following assessment time points and information should be collected and recorded as specified.

9.6 12 week assessment (+/-2 weeks) – standard practice 12 week scan*

- Pregnancy Confirmation (if not previously collected)
- Ultrasound (standard practice booking scan)
- Crown rump length
- Gestational Age
- Viable pregnancy assessment
- Congenital abnormality
- Concomitant medication review
- Pregnancy complications (if appropriate)
- Collect participant treatment diary (if not previously collected)
- Collect unused medication (if applicable/not previously collected)

9.7 20 – 24 week assessment – standard practice 20-24 week scan*

- Ultrasound
- Viable pregnancy assessment
- Gestational age
- Concomitant medication review
- Pregnancy complications (if appropriate)
- Congenital abnormality

9.8 Additional visits/scans as per standard practice*

If participant has an additional visit/ultrasound scan between 6 weeks - 20 week please record the following:

- Crown rump length (if recorded)
- Gestational Age
- Viable pregnancy assessment

9.9 End of pregnancy assessment or follow-up $(6 - 8 \text{ weeks post end of pregnancy > 24 weeks gestation})^*$

- Pregnancy outcome assessments
- Concomitant medication review
- Pregnancy complications (if appropriate)
- Postpartum Maternal and infant infections
- Maternal and infant infections 6 weeks post delivery

The end of pregnancy assessment should only be carried out for randomised participants who deliver a baby >24 weeks gestation. This will be the final follow up for the participant.

* These assessments may be conducted by telephone unless there is a clinical need for participants to be seen in hospital.

9.10 Payment

There are no payments for participation in this trial. We will reimburse hospital parking charges when women attend for their biopsy and biopsy results.

10. PHARMACOVIGILANCE

10.1 Definitions

Term	Definition
Adverse Event (AE)	Any untoward medical occurrence in a participant to whom a medicinal product has been administered, including occurrences which are not necessarily caused by or related to that product.
Adverse Reaction (AR)	An untoward and unintended response in a participant to an investigational medicinal product which is related to any dose administered to that participant. The phrase "response to an investigational medicinal product" means that a causal relationship between a trial medication and an AE is at least a reasonable possibility, i.e. the relationship cannot be ruled out. All cases judged by either the reporting medically qualified professional or the Sponsor as having a reasonable suspected causal relationship to the trial medication qualify as adverse reactions. It is important to note that this is entirely separate to the known side effects listed in the SmPC. It is specifically a temporal relationship between taking the drug, the half-life, and the time of the event or
Serious Adverse Event (SAE)	 any valid alternative etiology that would explain the event. A serious adverse event is any untoward medical occurrence that: results in death is life-threatening requires inpatient hospitalisation or prolongation of existing hospitalisation results in persistent or significant disability/incapacity consists of a congenital anomaly or birth defect Other 'important medical events' may also be considered serious if they jeopardise the participant or require an intervention to prevent one of the above consequences. NOTE: The term "life-threatening" in the definition of "serious" refers to an event in which the participant was at risk of death at the time of the event; it does not refer to an event which hypothetically might have caused death if it were more severe.
Serious Adverse Reaction (SAR)	An adverse event that is both serious and, in the opinion of the reporting Investigator, believed with reasonable probability to be due to one of the trial treatments, based on the information provided.
Suspected Unexpected Serious Adverse Reaction (SUSAR)	 A serious adverse reaction, the nature and severity of which is not consistent with the information about the medicinal product in question set out in the reference safety information: In the case of a product with a marketing authorisation, this could be in the summary of product characteristics (SmPC) for

that product, so long as it is being used within its licence. If it is
being used off label an assessment of the SmPCs suitability will
need to be undertaken.
in the case of any other investigational medicinal product, in the
investigator's brochure (IB) relating to the trial in question.

NB: "Severe" is often used to describe intensity of a specific event, which may be of relatively minor medical significance. "Seriousness" is the regulatory definition supplied above.

